C. Study Design flow. Primary care or mental health outpatient clinics agreeing to participate will be randomly selected (N=80 total) and initially offered REP for six months in order to implement LG. Based on previous research and preliminary data, it is expected that after six months of REP at least two-thirds of sites will be non-responsive to REP. The primary focus of the randomized comparisons in this study are sites that are initially non-responsive to REP (k=40), defined based on our preliminary studies as <10 patients receiving LG within six months of initiating REP and that patients received <75% group sessions. (Although not part of the primary randomized comparisons, sites that are responsive at 6 Months will continue to be followed and outcomes will be assessed). The non-responsive sites will be randomized 1:1 to receive additional External Facilitation (**REP+EF**) or External plus Internal Facilitation (**REP+EF/IF**). After another six months (at Month 12), sites that are still non-responsive (based on the same criteria) will be randomized 1:1 to either continue **REP+EF** or augmentation with IF (**REP+EF/IF**). All sites are followed for a total of 24 months. Patient-level outcomes will be assessed by study staff using assessments considered part of routine clinical care (e.g., symptoms and quality of life) starting at the initiation of REP and then at 6, 12, 18, and 24 months later among a pre-selected cohort of n=20 patients per site who are identified by site providers for LG (total patients participating in the project N=k*n=800). Patients receiving Life Goals as part of their routine clinical care may opt in or out in participating in the outcomes assessment component. As with our prior implementation work (R01 MH79994), independent evaluators (study staff who are not aware of the assignment to **REP+EF** or **REP+EF/IF**) will conduct study outcomes assessments to ensure consistency of

data collected across sites and to prohibit provider/site or investigator assessment bias. Pre-identification of LG recipients also maximizes consistency of the patient population across sites (see patient criteria below).

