The goal of the Secondary Aim 1 analysis is to determine whether continuing **REP+EF** versus augmenting with **REP+EF/IF** leads to changes in outcomes, among sites who are non-responsive at Month 12. This analysis is a comparison of cells B vs. C (Figure 2). Both primary and secondary longitudinal outcomes above will be examined using an LMM similar to that described above, except (a) including only the subset of sites that do not respond at Month 12 to **REP+EF**, (b) using monthly longitudinal outcomes from Month 12 to Month 24, and (c) the LMM will use dummy-indicators for time (i.e., time-saturated model since there are only 3 measurement times for each longitudinal outcome).

The Secondary Aim 2 analysis will involve an analysis of implementation costs. The implementation (REP, EF, IF) costs will be summed for each site as a measure of total costs and changes in costs will also be assessed over time (6, 12, 18, 24 months). An exploratory analysis of the incremental effectiveness of IF by comparing costs from sites given **REP+EF/IF** versus those with **REP+EF** will be conducted from the site's perspective. In regression models of costs, Generalized Linear Models with log link functions will be used to correct for heteroscedasticity and reduce the impact of outliers. Effectiveness will be measured by changes in health utilities using the SF-6 (a subset of SF-12 questions) as well as the Euro-QOL 5D. Cost-effectiveness will be calculated as the ratio of incremental average site-level cost and incremental average effectiveness (change in patient-level utilities) of IF. A standard nonparametric bootstrapping approach will be used to calculate confidence intervals and cost-effectiveness acceptability curves.

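### The cost-effectiveness ratio divides summed cost by a utility change with no time dimension, over no stated common horizon, so it cannot credit how long patients benefit

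*Combined protocol and SAP*

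**What the plan says.** The definition is in the Secondary Aim 2 paragraph of Section VI (Analyses and Evaluation).

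- Cost: "The implementation (REP, EF, IF) costs will be summed for each site as a measure of total costs". The same sentence adds that "changes in costs will also be assessed over time (6, 12, 18, 24 months").
- Effect: "Effectiveness will be measured by changes in health utilities using the SF-6 (a subset of SF-12 questions) as well as the Euro-QOL 5D".
- Ratio: incremental average cost at site level divided by "incremental average effectiveness (change in patient-level utilities) of IF".

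Bootstrap confidence intervals and acceptability curves are to follow. The analysis is labelled exploratory and takes the site's perspective. The documents mention no QALY, area under the curve or time horizon. They do not say between which visits the utility change is taken, or which months of cost enter the ratio.

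Two other places bear on this. The primary-aim paragraph of Section VI sets the main contrast for the SF-12 mental health score as change from Month 6 to Month 18, and says a Month 24 contrast will be examined there and in all later analyses. Section V.C (Study Design flow) says all sites are "initially offered REP for six months in order to implement LG". Non-responsive sites are then randomised at Month 6, and sites still non-responsive at Month 12 are randomised 1:1 to "either continue REP+EF or augmentation with IF". Section V.D confirms that this second randomisation concerns REP+EF sites.

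**The concern.** The numerator grows with time and the denominator does not. A utility gain that patients hold for a year and an equal gain that appears only at the last survey give the same ratio. A gain that comes and goes before the chosen visit counts for nothing.

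The design makes this more than a formality. In one arm the Internal Facilitator starts at Month 6. In the other, some sites get one from Month 12. Part of what early IF could buy is earlier benefit, and a change measured at a late visit cannot show that.

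Section II states the project's goal as building the most cost-effective adaptive strategy, and this ratio is the only planned analysis that joins cost to patient benefit. As defined, it is a cost per unit of utility change, not a cost per QALY. The acceptability curve would therefore have a willingness-to-pay axis that cannot be read on the QALY scale.

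**Working it through.** The plan gives no expected utility difference and no ratio, so there is no figure to reproduce. What follows is an illustration.

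**Inputs.** IF cost of $5,500 per site over 12 months (earlier trial, Section IV); 20 patients per site (Section V.C); surveys at Months 6, 12, 18 and 24 (Section V.F). Assumed: a between-arm utility difference of 0 at Month 6 and a gain of 0.05, with 0.02 and 0.10 as the range.

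**Formulas.** Cost per patient = 5,500 / 20 = $275. With half-year steps and between-arm differences d:

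QALY = 0.5 × (d6/2 + d12 + d18 + d24/2).

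The planned ratio is $275 divided by the difference at the chosen end visit.

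| Difference at Months 6, 12, 18, 24 | QALY | Cost per QALY | Planned ratio, Month 24 | Planned ratio, Month 18 |
|---|---|---|---|---|
| Held: 0, 0.05, 0.05, 0.05 | 0.0625 | $4,400 | $5,500 | $5,500 |
| Linear: 0, 0.0167, 0.0333, 0.05 | 0.0375 | $7,333 | $5,500 | $8,250 |
| Late only: 0, 0, 0, 0.05 | 0.0125 | $22,000 | $5,500 | undefined |
| Lost by Month 24: 0, 0.05, 0.05, 0 | 0.0500 | $5,500 | undefined | $5,500 |

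For example, held: 0.5 × (0 + 0.05 + 0.05 + 0.025) = 0.0625, and 275 / 0.0625 = $4,400. Late only: 0.5 × 0.025 = 0.0125, and 275 / 0.0125 = $22,000.

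The first three rows share a Month 24 change of 0.05 but differ up to 0.0625 / 0.0125 = 5-fold in QALYs. Across the assumed range, a gain of 0.02 gives $13,750 per unit against $11,000 to $55,000 per QALY; a gain of 0.10 gives $2,750 per unit against $2,200 to $11,000 per QALY.

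**IF cost in the REP+EF arm.** The $275 charges IF to one arm only. If every REP+EF site were non-responsive at Month 12, half would get IF under 1:1 allocation. If IF also cost $5,500 at each of those sites, the increment would fall to 5,500 × (1 − 1/2) = $2,750 per site, or $137.50 per patient. All the ratios scale by the same factor, so the five-fold spread is unchanged.

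**Per site or per patient.** The plan puts site-level cost over patient-level utility. At a gain of 0.05 that is 5,500 / 0.05 = $110,000 per unit, against 275 / 0.05 = $5,500 with cost per patient.

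**Run-in REP cost.** Add an equal expected REP cost R, and an equal other cost of $3,000, to both arms: (R + 3,000 + 5,500) − (R + 3,000) = $5,500 for any R. Only precision changes. With 20 v 20 sites and an assumed between-site SD of $1,000 for post-randomisation cost, SE = √(1,000² × 2/20) = $316. Adding run-in cost with an assumed SD of $1,000 gives √((1,000² + 1,000²) × 2/20) = $447.

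**The case against.** The strongest reply is that the plan is silent rather than wrong. It never says that the utility change is taken between two visits, nor that the cost in the ratio runs to Month 24. The four surveys and the costs by period would allow a matched, time-integrated analysis. Section VI also offers a default of Month 18 with Month 24 as follow-up, although the Month 18 contrast is stated for the SF-12 score and not extended to utilities. This stands: a reader might infer a stated two-visit change set against 24 months of cost, and the documents do not go that far.

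Taking Month 18 as the end visit would separate the held, linear and late-only paths. It would not cure the problem: the late-only path becomes undefined, and the held and lost paths give the same ratio although their QALYs are 0.0625 and 0.0500.

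A reader might also infer that REP cost from the run-in distorts the ratio. It does not. It arises before randomisation, has no expected difference between arms and cancels from the increment. Nor do the documents say that the arms will converge by Month 24: only REP+EF non-responders are re-randomised, and half of those are allocated IF.

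Finally, the plan promises no cost per QALY, so one may call this a preference. That carries less weight, given the stated goal of cost-effectiveness, the planned acceptability curves and the re-randomisation at Month 12. The exploratory label does limit the consequence.

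**Conclusion.** The concern holds in this form: the denominator of the ratio carries no duration of benefit, and no common horizon is stated for cost and effect. In the illustration, equal Month 24 changes correspond to up to five-fold different QALYs, and the planned ratio can be defined at one candidate visit and undefined at the other. The dollar figures rest on assumed utility gains and paths and on a cost from an earlier trial. The five-fold factor depends only on the assumed paths and the survey spacing, not on the size of the gain or the cost.

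The primary outcome, the randomised comparisons and the cost estimates themselves are untouched. This is a cheap improvement, of low priority because the analysis is exploratory.

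**What to change.** In the Secondary Aim 2 paragraph:

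- Define effectiveness as QALYs per patient over Months 6-24: the trapezoid area under the SF-6 utilities at Months 6, 12, 18 and 24, adjusted for Month 6 utility. Do the same for the Euro-QOL 5D if it is collected at those visits; Table 3 does not list it.
- Count incremental implementation cost over the same Months 6-24, including any IF cost at REP+EF sites after Month 12, and on the same per-patient basis.
- Report REP run-in cost separately as a description, to keep its noise out of the increment.

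The cost is a change of wording. The SF-6 items come from the SF-12, which is already surveyed at all four visits. The one downside is that patients with a missed visit need a model or imputation for the area under the curve.

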D. Site Organizational Randomization: The unit of randomization is the site and will be stratified using a minimization allocation method. This procedure will ensure that groups are balanced for site variables that may correlate highly with outcomes. The Month 6 randomization for REP non-responsive sites, will be stratified by state, type of practice (primary care or mental health site), and site-aggregated mean mental health related quality of life measured at Month 6. The Month 12 randomization for non-responders to **REP+EF** will be stratified by site-aggregated quality of life measured at Month 12. Based on interviews with site leaders and the literature, participating sites differ more by state and practice type than by type of network, and state and practice are correlated with mental health related quality of life and number of LG encounters.

E. Implementation Components (Table 1)

REP: All sites will receive REP (Table 1) in the first three months and will be monitored monthly up to the sixth month in the use of LG. REP includes dissemination of the LG package, training, and LG uptake monitoring for up to six months. REP includes an off-site trainer, which is neither an External nor Internal Facilitator. The following REP components were previously operationalized by study investigators (R01 MH79994):

Step 1: Dissemination of LG package, in-service, and patient selection: Each site will designate at least one provider with a mental health background (master’s in social work, nursing degree, or bachelor’s with two years’ experience in mental health psychosocial treatment) to implement LG (“LG provider”). Regional two-hour in-services will be provided by study investigators who will give an overview of LG including the evidence, and details on how to implement LG in their setting. During the in-service, the LG package will be disseminated and the REP trainer will coach the LG providers in pre-identifying a cohort of patients.

Table 1: Summary of REP, REP+EF, and REP+EF/IF Implementation and Fidelity Measures

Implementation Component	REP	REP+EF	REP+EF/IF
REP (REP)	All sites	Randomize to Non-Responding Sites	Randomize to Non-Responding Sites
Step 1: Disseminate package: LG in-service and identify appropriate patients using medical record review	√	√	√
Step 2: Train site providers in LG	√	√	√
Step 3: Monitor LG uptake via monthly reporting sheets	√	√	√
REP+External Facilitator (REP+EF)			

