Intent-to-treat. Every effort will be made to collect patient level outcomes across all 80 sites and patients (N=1600) to conduct the primary and exploratory analyses (see below). The 40 sites randomized at month 6 (total 800 patients) will be included in the intent-to-treat randomized sample. The Primary Aim analysis will compare strategies in non-responding sites (k=40) beginning with **REP+EF/IF** versus strategies beginning with **REP+EF** on longitudinal change in patient-level SF-12 mental health scores (MCS- primary outcome). This analysis is a comparison of cells A+B+C vs. D+E (Figure 2). For this analysis, the longitudinal outcome is SF-12 mental health scores measured at Months 6 (pre-randomization), 12, 18, and 24. The primary contrast is the between groups difference in change from Month 6 to Month 18. The follow-up contrast at Month 24 will also be examined in this and all subsequent analyses. Linear mixed models (LMM), also known as random effects models, fit with SAS PROC MIXED will be used to analyze the longitudinal data. LMMs use all available measurements, allowing subjects to have an unequal number of longitudinal observations and producing unbiased parameter estimates as long as unobserved values are missing at random. The analysis will fit a 3-level (repeated measures for each person clustered within site) LMM with fixed effects for the intercept, time, group, and a group-by-time interaction term, where group is an indicator of **REP+EF/IF** vs. **REP+EF**. The LMM will also include random effects for site and time, an unstructured within-person correlation structure for the residual errors, and it will adjust for the following pre-randomization measures collected through Month 6: state and type of practice (primary care- or mental health site). Model diagnostics will be used to determine the suitability of more parsimonious (e.g., autoregressive) correlation structures, and nonlinear (e.g., piecewise linear or quadratic) effects for time. LMMs similar to the above for the primary outcome will be conducted for the secondary outcomes: **REP+EF/IF** vs. **REP+EF** on change in number of LG encounters, functional impairment, and psychiatric symptoms.

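### The cost-effectiveness bootstrap names no resampling unit and does not pair site cost with patient utility, although sites are randomised; if patients are resampled, intervals are too narrow by an ICC-dependent amount

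*Combined protocol and SAP*

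**What the plan says.** The Secondary Aim 2 paragraph of section VI (Analyses and Evaluation) defines cost-effectiveness as a ratio. The numerator is the difference between groups in average cost per site. The denominator is the difference in average change in patients' health utilities. Implementation "costs will be summed for each site as a measure of total costs". The only inferential method given for the ratio is: "A standard nonparametric bootstrapping approach will be used to calculate confidence intervals and cost-effectiveness acceptability curves". The paragraph labels the comparison of the two Facilitation strategies exploratory.

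The design is clustered. Section V.D states: "The unit of randomization is the site and will be stratified using a minimization allocation method". Section V.C gives the allocation ratio ("The non-responsive sites will be randomized 1:1 to receive additional External Facilitation") and the cluster size, a "pre-selected cohort of n=20 patients per site". Section VI adds: "The 40 sites randomized at month 6 (total 800 patients) will be included in the intent-to-treat randomized sample".

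For the primary outcome, section VI does model the site level, through a "3-level (repeated measures for each person clustered within site) LMM". The analysis of sites still non-responsive at Month 12 borrows that model. Nothing carries the site level over to the bootstrap.

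**The concern.** In its ordinary form, a nonparametric bootstrap draws observations as if they were independent. Patients at one randomised site are not independent, and no patient has an implementation cost of their own. The sentence therefore cannot be carried out without a choice that the plan leaves open:

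1. Resample whole sites, each carrying its cost and its patients' utilities. This respects the randomisation.
2. Resample sites for cost and patients for utility, separately. The utility interval then ignores clustering, and the correlation between cost and effect is lost.
3. Attach each site's cost to its patients and resample the patients. One cost is then counted as 20.

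Under the second or third choice, the intervals and the acceptability curve would suggest more certainty about utility than about 20 sites per arm can support. Section V.F names the added cost of Internal Facilitation as the main worry of the sites that would use these results, so the curve is likely to be read closely.

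**Working it through.** **Inputs from the documents.** There are 40 randomised sites, allocated 1:1, so about 20 per arm, with m = 20 patients per site. Check: 40 × 20 = 800, which matches the stated randomised sample. The plan gives no interval width, coverage or ICC for this analysis, so there is no figure of its own to reproduce beyond that.

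**Assumption.** The ICC of change in utility is not given. I use 0.01 to 0.10.

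**Effect of resampling patients as independent.**

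- Design effect: DE = 1 + (m − 1) × ICC = 1 + 19 × ICC
- Width relative to the correct interval: 1/√DE
- Real coverage of a nominal 95% interval: 2Φ(1.96/√DE) − 1

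| ICC | DE | Width vs correct | Coverage |
|---|---|---|---|
| 0.01 | 1.19 | 92% | 92.8% |
| 0.02 | 1.38 | 85% | 90.5% |
| 0.05 | 1.95 | 72% | 84.0% |
| 0.10 | 2.90 | 59% | 75.0% |

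Example at ICC 0.05: DE = 1 + 19 × 0.05 = 1.95; √1.95 = 1.40; 1.96/1.40 = 1.40; coverage 84.0%. With only 10 analysed patients per site, DE = 1 + 9 × 0.05 = 1.45, and coverage is 89.6%.

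**Worst case for cost.** If each site's cost were copied to its 20 patients and those patients were resampled, the ICC of cost would be 1. Then DE = 20, width is 1/√20 = 22% of correct, and coverage is 34%.

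**Simulation check.** 600 simulated trials, 400 resamples each, 20 sites per arm, 20 patients per site, normal data, percentile limits. Widths are in SD units.

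| Incremental utility | Patients resampled: coverage (width) | Whole sites resampled: coverage (width) |
|---|---|---|
| ICC 0.01 | 92.3% (0.27) | 94.2% (0.29) |
| ICC 0.05 | 84.8% (0.27) | 93.7% (0.37) |
| ICC 0.10 | 75.8% (0.27) | 94.5% (0.45) |

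For site cost, copying to patients gave coverage of 30% to 33% (width 0.26). Resampling sites gave 91% to 94% (width 1.18). Across all runs, including one with ICC 0, whole-site resampling covered 92% to 95% for utility. It is thus close to nominal, and a little low for cost with 20 sites per arm.

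**Pairing.** For a willingness-to-pay value λ, the variance of incremental net benefit is λ²Var(ΔE) + Var(ΔC) − 2λCov(ΔE, ΔC), where ΔE and ΔC are the differences in utility and cost. Separate resampling sets the last term to zero. The direction of the resulting error depends on the sign of the covariance, which the documents do not give, so I put no size on it.

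**Limit of the check.** It covers the utility and cost differences one at a time. Neither the ratio interval nor the acceptability curve was simulated.

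**The case against.** The best defence is that the plan contains no stated error. The word *nonparametric* describes the distributional assumption, not the unit drawn. The surrounding text is about sites: costs are totalled per site, and the numerator is a site average. On a file with one row per site, an ordinary bootstrap is already a site bootstrap. The analysis is exploratory, and at an ICC of 0.01 or 0.02 patient resampling covers 92.8% or 90.5%, not far from the 91% to 95% that site resampling itself achieves here.

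Most of this stands. A reader might infer that the plan resamples patients as independent and that its intervals are therefore far too narrow. The documents do not support that: the resampling unit is unstated, a site-level reading is permissible, and no ICC is given. Nor may the 34% cost coverage be attributed to the plan, because nothing in it describes copying a site's cost to patients. It is also fair that the plan does not tie the cost-effectiveness groups explicitly to the Month 6 arms, and some sites are re-randomised at Month 12, so 20 sites per arm is an assumption for this analysis.

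What the defence does not answer is that the denominator is a patient-level measure and that no text links it to its site in the bootstrap. The valid procedure is one reading among several and is not written down.

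**Conclusion.** The point holds in a limited form. The plan names a standard bootstrap for a ratio that mixes site-level cost with patient-level utility in a site-randomised trial. It states neither a site-level resampling unit nor that cost and utilities stay together. If patients' utilities are resampled as independent, the utility interval has 92% to 59% of its correct width, and real coverage is 92.8% to 75.0%, over assumed ICCs of 0.01 to 0.10 with 20 patients per site. The shortfall thus runs from slight to serious, and it shrinks with fewer analysed patients per site. The 34% cost coverage is a worst case only. If sites are resampled, there is no narrowing beyond small-sample error. The primary SF-12 analysis models the site and is unaffected.

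**What to change.** Replace the standard bootstrap with a cluster bootstrap, stating that:

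- whole sites are drawn with replacement within each randomised arm, and which randomised groups (Month 6 arms or otherwise) are compared;
- each drawn site brings its cost and all its patients' utilities;
- the cost difference and the utility difference are both recomputed in every draw;
- the intervals and the acceptability curve come from the same replicates.

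Naming the interval type, with a small-sample adjustment for about 20 sites per arm, is an optional refinement. The change needs a sentence or two in the plan, a few lines of code and no new data. The price is wider intervals and a flatter acceptability curve wherever patients would otherwise have been resampled.
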